8. STATISTICAL

8.1. Description of planned statistical methods

Study population

All included subjects will be included in the analyses, which will be conducted according to the ITT principle.

Statistical analyses

An initial analysis of the data will provide a description of the overall population. The normality of the distribution of quantitative variables will be assessed using the Shapiro-Wilks normality test. Statistical results will be presented as means \pm standard deviations for quantitative variables with a Gaussian distribution, and as medians and interquartile ranges for other variables. For qualitative variables, frequencies and associated percentages will be presented. Qualitative variables will be compared using a chi-square test. If the conditions for conducting this test are not met, Fisher's exact test will be used. Quantitative variables will be compared between the two groups: for normally distributed variables, using a Student's t-test or an analysis of variance; for non-normally distributed variables, using a Wilcoxon-Mann-Whitney test.

Analysis of the primary outcome measure

Dysfunction rates will be estimated as point estimates and 95% confidence intervals.

Analysis of Secondary Endpoints

Depending on the rates of dysfunction observed, logistic regression will be used to estimate the variables associated with the risk of dysfunction. If the rate is too low for such modeling, descriptive analyses will be performed.

Modeling of dysfunction times over time may be performed using a Kaplan-Meier model. A Cox regression may be adjusted to determine the associated variables.

8.2. Expected number of participants to be included in the study, with statistical justification

Since the primary objective is to detect a non-zero rate of probe malfunction at the time of the procedure, we base the calculation of the sample size on the binomial distribution and the probability of observing no malfunctions in a sample of size n . Assuming a minimum malfunction rate of 1%, a study of 299 subjects yields a probability of observing no malfunctions that is less than an alpha risk of 5%. To account for unusable data and withdrawals of consent, we propose including a total of $N=330$ subjects in this study.

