4.2. Secondary endpoints

In relation to secondary objective 1:

Probe malfunction rate at the follow-up visit at M3 and M12 based on an abnormal impedance value (stimulation circuit and shock impedance) recorded during probe parameter testing.

In relation to secondary objectives 2 and 3:

Correlation between the probe malfunction rate and probe type and patient clinical variables.

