6.2.4. Follow-up at 3 months and 1 year post-procedure

A standard follow-up visit to check the defibrillator is scheduled 3 months (\pm 3 months) and 12 months (\pm 3 months) after the procedure. This follow-up involves testing the lead's standard parameters (sensitivity, pacing threshold, pacing impedance, and defibrillation impedance), as well as downloading the device's memory to ensure there have been no abnormal signals from the lead since the procedure.

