6.3. Study Design

Steps	Inclusion Visit	In the operating room	3 months post-procedure (± 3 months)	12 months post-surgery (± 3 months)
	Pre-procedure Pre-procedure cardiology visit			
Information	R			
Consent	R			
Verification of criteria inclusion and non-inclusion	R			
Testing the probe settings on the old housing		R		
Replacing the defibrillator		S		
Visual inspection of the connectors		S		
Testing the probe parameters before and after connecting to the new housing		S		
Testing the defibrillation circuit on the new unit		R		
Test of probe parameters at 3 months (± 3 months) and 12 months (± 3 months) post-procedure			S	S
Recording of any complications		S	S	S

R: Procedures, processes, and treatments added by the research;

S: Procedures, processes, and treatments related to care

6.4. Expected duration of participant involvement, description of the timeline and duration of the study

The study for a patient begins when the patient and the investigator sign the consent form and ends at the 12±3-month visit. For each patient, the duration of the study will therefore be 12 months (± 3 months).

The planned enrollment period is 24 months. The study is expected to take 39 months to complete, starting from the date of the first enrollment.

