8.5. Method for handling missing, unused, or invalid data

No specific method for imputing missing data is planned.

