12.5. Identification of all data to be collected in the observation log

Preoperative data:

- Age
- Gender
- Height
- Weight
- Medical history
- Data on first implantation

Intraoperative data:

- Result of probe parameter test
- Defibrillation circuit test result
- ICD impedance
- Any complications

Postoperative data:

- Results of the lead parameter test

13.FINANCING AND INSURANCE

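### Section 8.1 allows Kaplan-Meier and Cox for dysfunction times, but as collected a follow-up dysfunction is bracketed between checks, not dated; an interval-censored method fits the data

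*Combined protocol and SAP*

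**What the plan says.** Section 8.1 (secondary endpoints) permits two time-to-event methods: "Modeling of dysfunction times over time may be performed using a Kaplan-Meier model" and "A Cox regression may be adjusted to determine the associated variables". Both sentences are permissive.

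Section 4.2 gives the endpoint for secondary objective 1 as "Probe malfunction rate at the follow-up visit at M3 and M12 based on an abnormal impedance value". That is a status at a visit, not a date. The schedule in section 6.3 sets the windows: "Test of probe parameters at 3 months (± 3 months) and 12 months (± 3 months) post-procedure". The M3 visit can therefore fall anywhere from 0 to 6 months and the M12 visit from 9 to 15 months.

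Section 6.2.4 adds that each visit includes "downloading the device's memory to ensure there have been no abnormal signals from the lead since the procedure". The only postoperative item in the data list of section 12.5 is "Results of the lead parameter test". It names no date of dysfunction and no date of a memory signal.

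No section defines the failure date, the time origin or the censoring rule for these curves. On missing or invalid data, section 8.5 says only "No specific method for imputing missing data is planned".

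**The concern.** Kaplan-Meier and Cox need a failure time that is either known or right-censored. Here a lead that tests normal at surgery and abnormal at M3 failed somewhere in between, and likewise between M3 and M12. These are interval-censored data, and the plan names no method for them. With no event date collected, the obvious substitute is the date of the visit that found the failure. A lead that fails at month 1 and is read at month 5 would then enter the curve at month 5.

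Timing matters to this study. Section 2.1 cites a possible peak of failures within 3 months for one lead model, which is the period that visit dating distorts most. Cox would be used to look for associated variables (secondary objectives 2 and 3). The study is multicentre, so a centre or lead group that is seen earlier could appear to fail faster.

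**Working it through.** **The plan's own figure.** The sample size rests on the intraoperative endpoint: ln 0.05 / ln 0.99 = 298.07, so n = 299, and 0.99^299 = 0.0495 < 0.05. This reproduces and does not depend on the present point. The plan gives no figure for the time-to-event analysis.

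**Inputs.** The windows are 0–6 and 9–15 months (sections 6.2.4 and 6.3). The failure rate is 3.5% at 12 months, the one-year rate cited in section 2.1. Assumptions, because the documents give neither: constant hazard, visits uniform over a stated range, all visits attended, each failure dated at the visit that finds it, and non-failures censored at the M12 visit.

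λ = −ln(1 − 0.035)/12 = 0.00297 per month. The true cumulative failure is 1 − exp(−3λ) = 0.89% at 3 months and 3.5% at 12 months.

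**At 3 months.** Only patients whose M3 visit (V) has happened by month 3 can contribute, and only with failures up to that visit. To first order the estimate is P(V ≤ 3) × E[V | V ≤ 3] × λ, against a true 3λ.
- V uniform on 0–6: 0.5 × 1.5λ = 0.75λ = 0.22%, ratio 0.25.
- V uniform on 2–4: 0.5 × 2.5λ = 1.25λ = 0.37%, ratio 0.42.

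Visit dating can only delay an event, so with no censoring before month 3 the 3-month figure cannot exceed the truth.

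**At 12 months.** M3 visits centred on month 3 contribute 3λ. With M12 visits uniform on (a, b), those seen at time t bring on average t − 3 months of failures, while only patients not yet seen remain at risk. The visit-dated hazard is therefore λ(t − 3)/(b − t). Integrating from a to 12:

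H = λ{3 + (b − 3) ln[(b − a)/(b − 12)] − (12 − a)}, against a true 12λ.

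| M12 visits | H/λ | Estimate, 1 − exp(−H) | Ratio to 3.5% |
|---|---|---|---|
| 9–15 | 8.32 | 2.4% | 0.70 |
| 11–13 | 8.93 | 2.6% | 0.75 |
| 10–13 | 11.99 | 3.5% | 1.00 |
| 9–13 | 13.86 | 4.0% | 1.15 |
| 9–12.5 | 18.49 | 5.3% | 1.53 |

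Simulation with 2,000,000 patients per scenario agrees: 0.22% v 0.90% at 3 months and 2.43% v 3.51% at 12 months over the full windows; 5.29% v 3.50% at 12 months with M12 visits at 9–12.5.

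**Sensitivity (simulated).**
- Early peak, with 60% of the 12-month failures in months 0–3, full windows: 0.52% v 2.09% at 3 months (0.25) and 2.80% v 3.50% at 12 months (0.80).
- Late tail, constant hazard, full windows: 7.67% v 4.23% at 14.5 months, so too high.
- Visits exactly at 3 and 12 months: ratio 1.00 at both.
- Half of the failures dated from device memory, constant hazard, full windows: 0.63 at 3 months and 0.85 at 12 months. All dated: 1.00.

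**Cox.** Take two groups with the same true hazard, one seen a month earlier (M3 at 1–4 v 2–5, M12 at 10–13 v 11–14). The visit-dated hazard ratio is about 2.1 instead of 1. If only M3 timing differs it stays close to 1, so the distortion comes mainly from M12 timing.

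**Does the alternative help at this size?** In 500 simulated trials of 330 patients (constant hazard, full windows), an interval-censored Weibull was nearly unbiased. Compared with visit-dated Kaplan-Meier it cut root mean squared error from 0.71 to 0.51 percentage points at 3 months and from 1.50 to 1.03 at 12 months.

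**The case against.** The strongest reply is that little rests on these curves. Section 8.1 says they may be run, not that they will be. Objective 1 is met by the proportion abnormal at each visit, and no section assigns Kaplan-Meier to it. Those proportions do not depend on failure dates. Simulated over the full windows with a constant hazard they are 0.88% and 3.51%, against true rates of 0.90% and 3.50%. With the early peak they are 1.68% and 3.47%, against 2.1% and 3.5%; that M3 shortfall comes from the visit window, not from Kaplan-Meier. This objection stands and limits the point.

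A reader might infer that failures can be known only at the two visits. Section 6.2.4 does not support that: the memory download covers the time since the procedure and may date some failures. What remains is that section 4.2 does not bring memory signals into the endpoint and section 12.5 does not list their dates. That visit dates would be used instead is itself an inference from the plan's silence.

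A further objection is that the remedy gains little with so few events. At 3.5%, 330 × 0.035 = 11.6, or about 12 failures. For the Turnbull estimator alone this has force: in 150 simulated trials its root mean squared error was 0.77 against 0.70 points for visit-dated Kaplan-Meier at 3 months, and 1.26 against 1.40 at 12 months. A parametric interval-censored model does better, although the Weibull result above comes from a constant hazard, which favours it. The small event count limits any covariate regression, interval-censored or not.

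**Conclusion.** The point holds for the optional time-to-event analysis. The methods named need failure times that the endpoint definition and data list do not supply. If visit dates fill the gap, cumulative failure at 3 months is understated, to about 0.25 of the truth with visits over the full window and about 0.4 with visits within ±1 month. At 12 months the result ranges from about 0.7 to about 1.5 times the truth according to when M12 visits fall, and Cox can show a scheduling difference as a difference in risk.

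It is tempting to say that the curve is biased low at both landmarks. The documents do not support that: they give windows but no distribution of visits within them, and the 12-month direction turns on that distribution. Nor do they support saying that the primary endpoint or the M3 and M12 visit proportions are wrong.

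The sizes rest on a 3.5% rate at 12 months, the assumed hazard shape and visit distributions, full attendance and no dating from device memory. Any memory dating shrinks the error.

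**What to change.** In section 12.5, and so in the eCRF, list the date of each lead check and, where the device memory shows one, the date of the first abnormal signal.

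In section 8.1, replace the Kaplan-Meier and Cox sentences with a rule for any time-to-event analysis that is run:
- State the time origin and the censoring rule.
- Take the memory date as the failure time where there is one. Otherwise use the interval from the last normal to the first abnormal check.
- Estimate cumulative failure at 3 and 12 months with an interval-censored Weibull model, with the Turnbull estimator as a check on its shape.
- Limit any interval-censored regression to what about 12 events can support, and otherwise describe the failures.

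Dropping the time-to-event sentences would also resolve the mismatch, at the price of losing the failure pattern over time.

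The cost is SAP wording, one or two eCRF fields and intervals that show the real uncertainty about timing. The fields should be added while data are being collected, because the dates are harder to recover later.

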8.3. Expected significance level

A significance threshold of 5% will be used in the analyses.

8.4. Statistical criteria for study termination

No interim analysis is planned that could lead to the study being halted.

8.5. Method for handling missing, unused, or invalid data

No specific method for imputing missing data is planned.

8.6. Management of changes to the initial statistical plan

Any modification to this plan will be documented in writing, stating the reasons for the changes. The analysis plan and, if applicable, the document(s) modifying the initial statistical analysis plan will be appended to the analysis report.

9. DATA PROTECTION RIGHTS AND SOURCE DOCUMENTS

9.1. Data Protection

The processing of personal data for this research falls within the scope of Articles 53 through 61 of Law No. 78-17 of January 6, 1978, as amended, relating to information technology, files, and civil liberties; and the General Data Protection Regulation (EU) 2016/679 of the European Parliament and of the Council of April 27, 2016, on the protection of individuals.

In accordance with the requirements of the CNIL (Law on Information Technology, Data Files, and Civil Liberties) and the European General Data Protection Regulation (GDPR), participants in this research will be informed, via the information notice and the consent form, of the following rights:

- the nature and purpose of the data collected as part of the research, as well as the retention period for such data.
- the possibility of withdrawing from the study at any time and the retention, by the sponsor, of the information collected (unless otherwise indicated by the data subject).
- their rights of access, rectification, objection, restriction, erasure, and data portability with respect to the data collected as part of the research. These rights may be exercised at any time during the study either by submitting a request to the physician overseeing the participants in the study (who will contact the sponsor) or by submitting a request to the sponsor's Data Protection Officer.
- the option, in the event of a problem or disagreement, to file a complaint with the CNIL.

The sponsor (through the TEC or the investigators) undertakes to respond to any request for access to data within a maximum of one month. Furthermore, only personnel authorized by the sponsor (investigators, ARC, TEC) and representatives of health authorities may have access to this information.

9.2. Access to Data

The sponsor has obtained the agreement of all parties involved in the research to ensure direct access to all research sites, source data, source documents, and reports for the purpose of quality control and audit by the sponsor and/or the competent authorities.

Investigators shall make the individual documents and data strictly necessary for the monitoring, quality control, and audit of the research available to persons authorized by the sponsor in accordance with applicable laws and regulations (Articles L.1121-3 and R.5121-13 of the Public Health Code).

9.3. Source documents

Source documents are defined as any original document or item that serves as proof of the existence or accuracy of data or facts recorded during the research. They will be retained for 15 years by the healthcare facility where the research was conducted, in accordance with regulations.

9.4. Data Confidentiality

In accordance with the provisions regarding the confidentiality of data to which persons responsible for quality control of research involving human subjects have access (Article L.1121-3 of the Public Health Code), and in accordance with the provisions regarding the confidentiality of information concerning, in particular, the nature of investigational drugs, trials, the participants, and the results obtained (Article R. 5121-13 of the Public Health Code), individuals with direct access to this data shall take all necessary precautions to ensure the confidentiality of information regarding the participants, particularly with respect to their identity, as well as the results obtained. Those responsible for quality control, just like the investigators themselves, are bound by professional secrecy (under the conditions defined by Articles 226-13 and 226-14 of the Penal Code).

During the course of the research or upon its completion, the data collected on the participants and transmitted to the sponsor by the investigators (or any other specialized personnel) will be anonymized. Patients will be identified only by an identification number containing the center number, their study entry number, and their initials. These details are recorded in the observation log. The collected data are strictly confidential. They are accessed only by the medical team, persons duly authorized by the study sponsor, and, if necessary, by representatives of the competent health and judicial authorities. The identity of participants will not be disclosed in any report or publication resulting from this study.

The sponsor will ensure that each research participant has provided written consent for the access and use of their personal data, which is strictly necessary for the quality control of the research.

The sponsor declares that it will process the study data in accordance with CNIL reference methodology MR-001.

9.5. Registration in the national registry of individuals participating in human research

This registration is not required for this research.

10. QUALITY CONTROL AND ASSURANCE

10.1. Quality Control

The sponsor appoints a Clinical Research Associate (CRA) to conduct monitoring visits, who will ensure that:

- the rights, safety, and protection of research participants are ensured,
- the critical elements necessary for analyzing the primary and secondary objectives are present,
- the reported data are accurate, complete, and consistent with the source documents,
- the research is conducted in accordance with the protocol, the Sponsor's Standard Operating Procedures, Good Clinical Practice (GCP), and applicable laws and regulations.

Quality control for the trial is conducted under the sponsor's responsibility in accordance with its Standard Operating Procedures and in compliance with Good Clinical Practice (GCP), the latest revision of the Declaration of Helsinki, and applicable laws and regulations.

The investigator and members of his or her team agree to make themselves available during visits conducted by the ARC.

During these visits, the following items will be reviewed:

- Written informed consent;
- Compliance with the research protocol and the technical procedures defined therein;
- Quality of data recorded in the observation log: accuracy, missing data, consistency of data with "source" documents (medical records, appointment logs, original laboratory results, etc.).

10.2. Quality assurance

Quality control of the trial is carried out under the responsibility of the Ambroise Paré Clinical Research Center. An audit may be conducted at any time by individuals appointed by the sponsor and independent of the research leaders. Except in special cases, the investigator is informed sufficiently in advance of the planned audit. The same applies to an inspection conducted by the Competent Authority. The purpose of these procedures is to ensure the quality of the research, the validity of its results, and compliance with applicable laws and regulations.

Those who direct and oversee the research agree to comply with the requirements of the sponsor and the Competent Authority regarding an audit or inspection of the research.

11. ETHICAL CONSIDERATIONS

11.1. Statement indicating that the research will be conducted in accordance with the protocol, good clinical practice, and applicable laws and regulations

The protocol complies with the ethical principles established by the^{18th}World Medical Assembly (Helsinki 1964) and by the amendments established at the^{29th}(Tokyo 1975),^{35th}(Venice 1983),^{41st} (Hong Kong 1989),^{48th}(Somerset West 1996),^{52nd}(Edinburgh 2000),^{53rd}(Washington 2002),^{55th}(Tokyo), 59th (Seoul), and revised at the 64thth World Medical Assembly (Fortaleza, Brazil, October 2013) . It will be conducted in accordance with the ICH guidelines on Good Clinical Practice.

11.2. Procedures for Informing and Obtaining Consent from Research Participants

No interventional research may be performed on a person without their free and informed consent, obtained in writing after all relevant information has been provided to them orally and in writing and prior to any procedure specified in the protocol and related to the research.

The research is presented orally to the patient by an investigator during the pre-procedure cardiology consultation. During this visit, patients receive information in understandable terms regarding the study's objectives and constraints, potential risks involved, necessary monitoring and safety measures, their right to refuse to participate in the study, and the possibility of withdrawing at any time without this affecting the care they receive. An information sheet corresponding to the information provided to the patient is given to the patient. After answering any questions the patient may have, and after ensuring that the patient has had sufficient time to reflect, the investigator obtains the patient's consent before enrolling the patient in the study.

A copy of the consent form, dated and signed by the person participating in the research as well as by the investigator, is provided to the person prior to their participation in the research. The investigator retains the original copy of the person's dated and signed consent form.

Changes to the protocol that result in an amendment shall be reflected by corresponding changes in the informed consent form and the information provided verbally to the patient.

